4.3.2 Endpoints related to safety/tolerability during the treatment period

- 1. Occurrence of adverse events from visit V1 to V6 [SAESEQ]
- 2. CIWA-Ar-Score, values for blood pressure and pulse for screening and visits 1 to 6 [CIWA].

5 MISSING VALUES AND OUTLIERS

5.1 MISSING VALUES

If missing values occur for the primary endpoint (e.g. due to protocol regulations or withdrawal of consent), these will be replaced after reviewing the data using suitable methods.

Additionally, sensitivity analyses will be conducted, including a complete-case analysis (where only participants with all data required for calculating the primary endpoint are analyzed) and, if necessary, data imputation using suitable methods.

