2 ANALYSIS POPULATIONS

2.1 DEFINITIONS

The intent-to-treat population (ITT) to be analyzed comprises all randomized subjects who were administered the investigational product (excluding the placebo lead-in medication and alcohol) at least once. The statistical analysis of this population determines whether the results are statistically significant or statistically non-significant.

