- 4. Alcohol craving in daily life will be measured using the "Obsessive Compulsive Drinking Scale" (OCDS, from obsessive [OCDSO], compulsive [OCDSK] and total score [OCDST]) before both self-administration experiments (V2 and V5) to compare treatment-related changes between the 3 treatment arms
- 5. Violations of the imposed abstinence are recorded as the proportion (%) of days with alcohol consumption detected (by TLFB) [VABST] to compare them between the three treatment arms and to investigate their influence on the primary endpoint.
- 6. Motivation to change drinking habits. The "Readiness to change" questionnaire is used to determine which of the three stages of change in drinking habits the participants are currently assigned to. Subscores of the Pre-Contemplation [RTCP], Contemplation [RTCC] and Action [RTCA] will be anlyzed. Differences between the stage of change before the study (screening), after completion of the study procedures (visit 6) and after completion of the brief intervention (telephone follow-up) will be considered independently of the treatment arm. The number of participants for whom the readiness to change increases, remains the same and decreases will be described.
- 7. Drinking habits will be assessedusing the Timeline follow-back interview (TLFB) at screening (or re-screening), at visits 1, 3 and 6 and at the telephone follow-up. Changes in drinking habits as a result of study participation will be recorded by comparing the drinking amounts during the 45 days prior to the start of the study (measured at the screening or re-screening) with those after the end of the study (telephone follow-up interview). The following points will be examined in each of the 3 treatment arms:
 - a) the percentage of drinking days [TFbITT],
 - b) the average amount drunk per drinking day [TFbIAVE],
 - c) the percentage of days with heavy alcohol consumption (over 60 g for men and 48 g for women = "binge days") [TFbIBT], and
 - d) the average amount of alcohol on these binge days [TFbITM]

- 8. Determine whether participants have ever received addiction treatment services [SSBNY] (e.g., addiction-specific counseling/treatment by an addiction counseling center or general practitioner or psychologist or psychiatric specialist or hospital) in comparison before study participation (for screening) and afterwards (visit 6 and telephone follow-up interview)

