6 STATISTICAL ANALYSES

6.1 PATIENT AVAILABILITY

The primary analyses will be conducted based on the intention-to-treat population (ITT). Additionally, per-protocol analyses will be conducted as secondary analyses to evaluate the effects of the intervention under ideal conditions.

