6.3 EXPOSURE TO THERAPY AND COMPLIANCE

Randomization will be stratified according to the two criteria:

- a) Severity of addiction characteristics up to the time of V4
 - "High" if there is at least a moderate alcohol use disorder according to DSM-5, i.e., the presence of at least 4 of the 11 criteria, or if significant physical alcohol withdrawal symptoms were reported anamnestically or observed by study physicians (CIWA at V3 or V4 > 6 points).
 - "Low" if there is only a mild alcohol use disorder according to DSM-5, i.e., the presence of no more than 3 of the 11 criteria, and physical withdrawal symptoms were neither reported anamnestically nor observed by physicians..

b) Answer to the question at time V4 as to whether patients want to reduce their alcohol consumption ("yes" or "no")

This stratification aims to ensure that the distribution of these two characteristics does not differ between the three treatment arms before the start of treatment.

It is hypothesized that acamprosate will have a more pronounced effect the more severe the addiction-related pathological changes in the reward system are. This aspect is captured by the composite factor "Severity of Addiction Characteristics" (criterion a).

Since the overwhelming majority of acamprosate studies in humans only included patients who wanted to reduce or stop their alcohol consumption, the clinical efficacy insights of acamprosate are limited to this group. On the other hand, it seems

inappropriate to make the desire for reduction a prerequisite for participation, as based on animal experiments and the observations of Mason et al. (2006), acamprosate reduces alcohol consumption even when there is no explicit desire for change, especially under the specific conditions of prior enforced abstinence.

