6.4 CONFIRMATORY ANALYSIS

Testing the two primary hypotheses

- H1: The administration of acamprosate compared to placebo leads to a significant reduction in the willingness to perform work in the laboratory experiment to obtain alcohol
- H2: The administration of calcium ions compared to placebo leads to a significant reduction in the willingness to perform work in the laboratory experiment to obtain alcohol infusions

Will be conducted using t-tests if the data is normally distributed. The test for normal distribution will be assessed using the Shapiro Wilk test and a graphical inspection of the distribution in the histogram. If the data is not normally distributed, Mann-Whitney tests will be used. The significance level is 0.025, as two null hypotheses are tested in the confirmatory analysis.

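### SAP 5.1 leaves the replacement of missing primary-endpoint values open until the data have been reviewed, and 6.4 tests the unadjusted change by a test picked from a normality pretest; one prespecified adjusted model with a named missing-data method should replace both

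*SAP*

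**What the plan says.** Section 2.1 defines the ITT population as randomised subjects dosed at least once and adds: "The statistical analysis of this population determines whether the results are statistically significant or statistically non-significant". Section 6.1 makes ITT the primary analysis. Attendance at V5 is required only for the per-protocol set (section 2.2), so a subject with no V5 experiment stays in the deciding analysis without a V2-V5 difference.

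For such values section 5.1 states that "these will be replaced after reviewing the data using suitable methods". The next sentence commits to sensitivity analyses: a complete-case analysis and, "if necessary, data imputation using suitable methods".

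Section 6.4 tests each active arm against placebo at 0.025. The test depends on the data: "The test for normal distribution will be assessed using the Shapiro Wilk test and a graphical inspection of the distribution in the histogram". And: "If the data is not normally distributed, Mann-Whitney tests will be used". No covariates enter.

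Section 6.3 stratifies randomisation by two factors known at V4, one of them "Severity of addiction characteristics up to the time of V4". Randomisation therefore follows V2, and V5 is the value at risk.

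**The concern.** Two choices in the confirmatory analysis are left open: how a missing V5 value is filled, and which test is applied. Both can be settled with data in view. Section 5.1 foresees at least two different reasons for missingness, protocol rules and withdrawal of consent, yet gives no assumption for either. Because primary and sensitivity imputation share one label, a reader cannot tell which imputed result is the deciding one. Methods that could all be called suitable can give different verdicts on the same data, and at least one of them breaks the stated error rate. The unadjusted change also makes poor use of the V2 measurement and the two strata, which are known before treatment starts.

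**Working it through.** **The plan's own figure.** Two hypotheses, each at 0.05 / 2 = 0.025. This reproduces section 6.4. The overall 0.05 is assumed, since the SAP does not state it.

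**Assumed inputs, none given in the SAP text available.** 30 per arm; SD of change 74; two-sided 0.025; V5 missing completely at random at 5, 15 or 25%; V2-V5 correlation 0.5 with equal SDs at both visits. The true effect used for power is the 60 work trials that section 1.1 calls relevant.

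**Error rate under own-arm-mean filling.** With n = 30 and r observed per arm, the filled mean equals the observed mean, so its true standard error uses r. The t-test computes its standard error from n and from a shrunken variance. The ratio of computed to true standard error is √[((r − 1)/(n − 1)) × (r/n)], and the critical value is t(58) = 2.301.

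| Missing | r | Ratio | Effective cut-off | False rejection, formula | Simulated, normal data |
|---|---|---|---|---|---|
| 5% | 28.5 | 0.949 | 2.184 | 0.033 | 0.034 |
| 15% | 25.5 | 0.847 | 1.950 | 0.057 | 0.056 |
| 25% | 22.5 | 0.746 | 1.716 | 0.093 | 0.100 |

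The formula column refers the effective cut-off to t with 2r − 2 degrees of freedom. With log-normal data the simulated rates are 0.026 / 0.055 / 0.095. Complete case and no-change, pooled-mean or placebo-mean filling stay at 0.018-0.028.

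**Does the choice alter the verdict?** With own-arm mean left out and a true effect of 60, complete case and the three other fills disagreed on significance in 4.5 / 15 / 23% of 1,500 simulated trials at 5 / 15 / 25% missing.

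**Does filling alter the test?** Shapiro-Wilk at 0.05 in each of the two arms, histogram not modelled:
- Normal data: at least one arm is flagged in 9-11% of trials with full data, and in 12-13 / 26-35 / 59-70% after single-value filling.
- Log-normal data (log-SD 0.8): about 88% with full data, 91-99% after filling, so the test used hardly changes.

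**Power at 15% missing.** With r = 25.5 per arm:
- Unadjusted change, complete case: standard error 74 × √(2/25.5) = 20.7; 60 / 20.7 = 2.90; power 0.72.
- Adjusted for V2: residual SD 74 × √((1 + 0.5)/2) = 64.1; standard error 64.1 × √(2/25.5) = 17.9; 60 / 17.9 = 3.34; power 0.85.

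Simulation gives 0.72 for the unadjusted complete-case t-test, 0.84 for the adjusted model on complete cases and 0.84 with multiple imputation. At correlation 0.3 the three figures are 0.71 / 0.89 / 0.88; at 0.7 they are 0.72 / 0.79 / 0.79.

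**The case against.** **There is a safeguard.** A complete-case analysis is prespecified, and the per-protocol set requires V5. True, and useful to the reader of the results. Both are secondary, however, so neither settles the result that section 2.1 says decides significance.

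**A reader might infer that the review is unblinded.** The SAP does not say so. The trial is double-blind, and own-arm-mean filling needs arm-level data. What stands is that section 5.1 does not state blinding and does not exclude that method.

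**A reader might infer that the test switch is a second source of error.** Section 6.4 does not say that filled data are checked for normality. Filling followed by the pretest stays near 0.025 for no-change, pooled-mean and placebo-mean filling. Own-arm mean inflates without the switch: the pretest adds nothing at 5% (0.034 both ways) and raises the rate to 0.071 and 0.140 at 15 and 25%. A multiple-imputation draw leaves no spike at a single value. The switch is a matter of undefined procedure, and mainly for near-normal data.

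**A reader might infer bias from the shrunken estimates.** No-change, pooled-mean or placebo-mean filling turns a true 60 into 60 × (1 − missing rate) = 57 / 51 / 45. Part of this is a different question: no-change and placebo-mean filling credit a subject without V5 data with no drug effect, which can be a legitimate target.

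**The adjusted model goes beyond curing section 5.1, and the sample-size basis is not in view.** It does go further. But it estimates the same contrast in work trials, its residual variance given V2 cannot exceed that of the change score, and it removes the test choice along with the open fill.

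**Conclusion.** The point stands as a weakness in prespecification that should be fixed; it does not show that the trial's error rate is inflated as planned. The wording defect needs no assumptions: no primary method, no assumption, no statement on blinding, one label for two roles, and no statement of which data the normality check uses.

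The sizes are illustrative. About 3.4 / 5.6 / 10% false rejection is the worst case among the fills examined. That the other fills hold 0.025 depends on completely random loss: under an assumed drinking-related placebo dropout at 15% missing, even the complete-case t-test reached 0.034. With very few missing V5 values the practical effect would be small. The power gain from about 0.72 to 0.84 depends on the assumed correlation and comes from baseline adjustment. Only the SAP was available; a rule in the protocol cannot be excluded, but section 5.1 refers to none.

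**What to change.** Before unblinding:

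1. Make the confirmatory analysis one prespecified linear model of V5 CATALC on arm, V2 CATALC and the two randomisation strata, with robust standard errors (for example HC2), reporting each adjusted difference from placebo in work trials at 0.025. Keep Mann-Whitney as a sensitivity analysis.
2. In section 5.1, replace the data-review wording with one primary missing-data method and its assumption, for example multiple imputation under missing at random using the model's variables, pooled by Rubin's rules. Exclude single mean imputation.
3. Keep the complete-case analysis and add one named analysis for values missing not at random, such as a reference-based or no-change one, clearly distinct from the primary method.

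Drinking data from the timeline follow-back at V3 (section 4.3.1 schedules it "at visits 1, 3 and 6 and at the telephone follow-up") may be added to the imputation model. No benefit is claimed, because any benefit rests on an assumed dropout mechanism.

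The cost is a few lines of SAP text and modest programming. The downside is that the method can no longer be chosen late.

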5.2 OUTLIERS

A Separate analysis of outliers is not planned.

6 STATISTICAL ANALYSES

6.1 PATIENT AVAILABILITY

The primary analyses will be conducted based on the intention-to-treat population (ITT). Additionally, per-protocol analyses will be conducted as secondary analyses to evaluate the effects of the intervention under ideal conditions.

6.2 DEMOGRAPHICS AND BASELINE CHARACTERISTICS

These data will be analyzed descriptively. For continuous variables such as age, the mean and standard deviation will be calculated. For categorical variables such as gender and partnership status, frequencies and percentages will be calculated.

For laboratory parameters ALAT, ASAT, LIPASE, CREA, eGFR, QUICK and CALCIUM, the central tendencies (mean or median) and the variability (standard deviation or interquartile range) will be calculated. For non-normally distributed data, non-parametric tests will be used for comparison between the subgroups. The normal distribution will be tested using the Kolmogorov-Smirnov test.

The FTND, AUDIT, ADS, BIS and SURPS questionnaires will be analyzed according to their respective scoring guidelines. The resulting scores will be described descriptively with mean and standard deviation and compared between the groups using ANOVA or Kruskal-Wallis test, depending on data distribution.

The vital parameters such as pulse, blood pressure, height and weight will be also analyzed descriptively. Group comparisons, e.g. between sex or age groups, will be conducted using t-tests or Mann-Whitney U-tests, depending on the data distribution; comparisons between treatment groups will be performed using ANOVA or Kruskal-Wallis tests, depending on the data distribution.

6.3 EXPOSURE TO THERAPY AND COMPLIANCE

Randomization will be stratified according to the two criteria:

- a) Severity of addiction characteristics up to the time of V4
 - "High" if there is at least a moderate alcohol use disorder according to DSM-5, i.e., the presence of at least 4 of the 11 criteria, or if significant physical alcohol withdrawal symptoms were reported anamnestically or observed by study physicians (CIWA at V3 or V4 > 6 points).
 - "Low" if there is only a mild alcohol use disorder according to DSM-5, i.e., the presence of no more than 3 of the 11 criteria, and physical withdrawal symptoms were neither reported anamnestically nor observed by physicians..

b) Answer to the question at time V4 as to whether patients want to reduce their alcohol consumption ("yes" or "no")

This stratification aims to ensure that the distribution of these two characteristics does not differ between the three treatment arms before the start of treatment.

It is hypothesized that acamprosate will have a more pronounced effect the more severe the addiction-related pathological changes in the reward system are. This aspect is captured by the composite factor "Severity of Addiction Characteristics" (criterion a).

Since the overwhelming majority of acamprosate studies in humans only included patients who wanted to reduce or stop their alcohol consumption, the clinical efficacy insights of acamprosate are limited to this group. On the other hand, it seems

inappropriate to make the desire for reduction a prerequisite for participation, as based on animal experiments and the observations of Mason et al. (2006), acamprosate reduces alcohol consumption even when there is no explicit desire for change, especially under the specific conditions of prior enforced abstinence.

6.4 CONFIRMATORY ANALYSIS

Testing the two primary hypotheses

- H1: The administration of acamprosate compared to placebo leads to a significant reduction in the willingness to perform work in the laboratory experiment to obtain alcohol
- H2: The administration of calcium ions compared to placebo leads to a significant reduction in the willingness to perform work in the laboratory experiment to obtain alcohol infusions

Will be conducted using t-tests if the data is normally distributed. The test for normal distribution will be assessed using the Shapiro Wilk test and a graphical inspection of the distribution in the histogram. If the data is not normally distributed, Mann-Whitney tests will be used. The significance level is 0.025, as two null hypotheses are tested in the confirmatory analysis.

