1 STUDY BACKGROUND

1.1 STUDY OBJECTIVES

The main research question is whether the current "Behavioral Test for the Development of medications for Alcohol Dependence" (TEMA) can demonstrate that the administration of acamprosate or ionized Calcium (Ca^{2+} = finished drug Calcium-Verla®) reduces the willingness to work for alcohol in a laboratory experiment following a 15- to 20-day period of alcohol abstinence.

The willingness to work for alcohol is determined by the cumulative number of work trials in the "constant attention task" (CAT). The change in this willingness due to the administration of acamprosate, Ca²⁺, or placebo is expressed as the difference in the cumulative number of work trials in the CAT per test day between Visit 2 (without medication) and Visit 5 (after administration of scamprosate, Ca²⁺ or placebo).

The hypothesis to be tested is that the administration of acamprosate compared to placebo or the administration of calcium ions compared to placebo, leads to a significant reduction in the willingness to work in the laboratory experiment to obtain alcohol.

Based on literature reports that form the basis of the sample size calculation, a relevant change is considered to be a reduction in blood alcohol concentration (BAC) of at least 0.1 per mille in one of the active treatment groups between Visit 2 and Visit 5 compared to the placebo group. In terms of the primary endpoint, this corresponds to a reduction in the cumulative number of work trials for alcohol infusions by 60.

Secondary objectives

The study aims to investigate whether:

- 1. the administration of acamprosate or calcium ions (Ca^{2+} = ready-to-use drug Calcium-Verla®) compared to placebo leads to altered subjective perception of alcohol effects
- 2. the efficacy of acamprosate or calcium ions can be predicted by basal levels or the change over time in measures of body calcium reserves reflecting a possible calcium deficiency
- 3. the administration of acamprosate or calcium ions reduces alcohol craving in daily life
- 4. the frequency of reported alcohol consumption during the imposed abstinence period differs between the treatment groups and how this affects the willingness to work for alcohol after the imposed abstinence period
- 5. participation in the study promotes the motivation to change drinking habits or alters drinking habits or the utilization of addiction treatment services

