4.2 PRIMARY ENDPOINT

The primary outcome measure is the difference in the cumulative number of work trials for alcohol in the "constant attention task" (CAT) [CATALC] between the first (V2) and second (V5) self-administration experiment, compared between the acamprosate vs. placebo and calcium vs. placebo treated groups [MED].

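### The confirmatory test uses V2 only by subtraction and leaves out both randomisation strata; adjusting both the t-test and the Mann-Whitney branch for them is a cheap possible gain in precision

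*SAP*

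**What the plan says.** Section 4.2 defines the primary outcome as the "difference in the cumulative number of work trials for alcohol in the" attention task between the two self-administration sessions. Section 1.1 describes this change as taken "per test day between Visit 2 (without medication) and Visit 5", so V2 is a pre-treatment measurement.

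Section 6.4 says that testing the two hypotheses "Will be conducted using t-tests if the data is normally distributed", and otherwise by Mann-Whitney, each at 0.025. On the choice between them, "The test for normal distribution will be assessed using the Shapiro Wilk test" together with a look at the histogram. No covariate is named in either branch.

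Section 6.3 states: "Randomization will be stratified according to the two criteria". These are severity (high or low, judged up to V4) and the wish to drink less (yes or no, asked at V4). Neither factor appears in a named analysis. The sensitivity analyses of section 5.1 deal with missing data ("Additionally, sensitivity analyses will be conducted, including a complete-case analysis"). Section 6.5.1 uses covariates for the subjective-effects analysis and plans exploratory regressions of the primary endpoint on calcium measures and abstinence violations, but names neither V2 nor the strata. The subgroups of section 6.6 are gender and ICD-10 dependence.

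**The concern.** Subtracting V2 is the best use of it only if its regression slope on V5 is 1. The efficient slope is rho × SD(V5)/SD(V2). With equal SDs this is rho itself, so it is below 1, and the change score then carries more of the V2 noise than it needs to.

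Stratified allocation removes between-arm variation due to the strata, but an analysis that ignores them leaves that variation in the standard error. To the extent that the strata predict the outcome, the test becomes conservative.

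At stake is the precision of two contrasts that are already tested at a split level, with data that the trial collects anyway.

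**Working it through.** **Inputs.** From the SAP: 0.025 per hypothesis (6.4); two binary strata (6.3); a relevant effect, about which section 1.1 says "this corresponds to a reduction in the cumulative number of work trials for alcohol infusions by 60". There is no design figure to reproduce, because N, SDs, rho, power, sidedness and allocation ratio are not in the SAP. Assumed here: two-sided 0.025, three equal arms, and 80% power for the t-test on change.

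**1. Adjusting for V2, normal data.** Let k = SD(V5)/SD(V2). In units of the V2 variance:
- Var(change) ∝ 1 + k² − 2·rho·k
- Var(adjusted) ∝ k²(1 − rho²)
- For k = 1 the ratio is (1 − rho²)/(2 − 2·rho) = (1 + rho)/2.

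Power after adjustment is Φ(3.083/√ratio − 2.241), with 3.083 = 2.241 + 0.842. As an illustration, if 60 trials were detectable with 80% power, SE = 60/3.083 = 19.5 and the 97.5% CI half-width is 2.241 × SE = 43.6 trials; adjustment multiplies it by √ratio.

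| rho (k = 1) | variance ratio | power | half-width (trials) |
|---|---|---|---|
| 0.3 | 0.65 | 94.3% | 35.2 |
| 0.5 | 0.75 | 90.6% | 37.8 |
| 0.7 | 0.85 | 86.5% | 40.2 |
| 0.9 | 0.95 | 82.2% | 42.5 |

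Simulation of the full model with non-prognostic strata at 12, 20 and 40 per arm agrees with these powers to within about 1 point.

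**2. Where the gain vanishes.** The ratio reaches 1 when rho·k = 1. At k = 1.2 it is 0.966 for rho 0.7 (0.7344/0.76) and 0.997 for rho 0.8 (0.5184/0.52). At k = 0.8 the gain is larger (ratio 0.50 to 0.64 for rho 0.3 to 0.9). With rho·k = 1, simulation with stratified blocks showed no loss at 20 and 40 per arm and 0.3 to 0.5 points lost at 12. If the allocation does not balance the strata, the closed form gives losses of 0.7, 1.5 and 2.9 points at 40, 20 and 12 per arm.

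**3. The strata.** If they explain a share R² of the residual variance and are left out, the actual type I error is 2(1 − Φ(2.241/√(1 − R²))). Power is Φ(0.842/√(1 − R²)) without them and Φ(3.083/√(1 − R²) − 2.241) with them.

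| R² | type I error, strata omitted | power without | power with |
|---|---|---|---|
| 2% | 0.0236 | 80.2% | 80.9% |
| 5% | 0.0215 | 80.6% | 82.2% |
| 10% | 0.0181 | 81.3% | 84.3% |

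The gain is about 1 to 3 points.

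**4. Against the whole planned procedure.** Steps 1 to 3 compare with the t-test only. The plan also has a Mann-Whitney branch, so the two-branch procedure was simulated with Shapiro-Wilk per arm at 0.05 as the switch (assumed), k = 1, non-prognostic strata, and the effect set for 80% t-test power (Monte Carlo SE about 1 point). Planned procedure v ANCOVA alone:

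| data | per arm | rho 0.5 | rho 0.7 | rho 0.9 |
|---|---|---|---|---|
| exponential | 20 | 86% v 89% | 90% v 85% | 91% v 80% |
| exponential | 40 | 91% v 90% | 94% v 87% | 95% v 83% |
| t, 3 df | 40 | 93% v 92% | 95% v 88% | 96% v 87% |

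At 12 per arm with exponential data, ANCOVA led at rho 0.5 (87% v 83%), tied at 0.7 and lost at 0.9 (81% v 88%).

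**5. Both branches adjusted.** Here ANCOVA is used, or Mann-Whitney on covariate-adjusted residuals when the residuals are non-normal. Across the cases run for this comparison, power against the plan was 82-91% v 79-81% (normal), 92-99% v 87-96% (exponential) and 94-99% v 90-95% (t, 3 df), with type I error about 0.02 to 0.03.

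**The case against.** The strongest objection is that the plan is not a bare t-test. Its Mann-Whitney branch protects power when the data are skewed or heavy-tailed. That is a live possibility: the outcome is a count, and section 2.3 foresees participants who ask only for saline at V5. A reader might infer that ANCOVA should simply replace the planned tests at no cost. Step 4 shows otherwise. This objection stands, and it is why the fix keeps two branches.

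Other points that stand in part:
- The t-test uses two arms (2n − 2 df), whereas the three-arm model borrows residual variance from the third (3n − 6 df). At 12 per arm, three-arm v two-arm ANCOVA gave 84% v 81% at rho 0.7 and 79% v 74% at rho 0.9, so part of a small-sample gain is not covariate adjustment.
- The headline gains assume k = 1; for k somewhat above 1 and high rho they are close to nil.
- Section 6.3 argues for severity as an effect modifier ("It is hypothesized that acamprosate will have a more pronounced effect the more severe the addiction-related pathological changes in the reward system are") and gives no evidence that either stratum predicts the outcome.
- The large-sample guarantee for the common-slope model assumes equal allocation and a V2 slope shared by the arms. The protocol, not shown, may settle the allocation.

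A reader might also infer that the planned test is biased or has an inflated error rate. The SAP does not support that. Randomisation makes the unadjusted comparison of changes unbiased, the level is split between the two hypotheses, and leaving out prognostic strata makes the test conservative. Nor can it be inferred that the trial is underpowered, since no design figures are given.

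**Conclusion.** The point holds as a cheap improvement, not as an error. V2 is used with a fixed slope of 1, and the strata are used in the allocation but in no named analysis. With roughly normal data and equal SDs, adjustment for V2 is worth about 2 to 14 points of power from a base of 80%, depending on rho; the strata add about 1 to 3 points if they explain 2 to 10% of residual variance. The true gain may be nil and is unknown without rho and the SDs.

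The gain survives non-normal data only if the rank branch is adjusted too. That version matched or beat the plan in the simulated cases of step 5, which is evidence over a limited range and not a general proof. In very small, strongly skewed arms with high rho, and strata that the allocation does not balance, it could still fall a few points short.

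**What to change.** Before unblinding, reword section 6.4 as follows.

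- **Primary model:** a linear model of V5 CATALC on arm, V2 CATALC, severity stratum and wish-to-reduce stratum. Report the two active-minus-placebo contrasts with confidence intervals, each tested at 0.025. Modelling the change instead gives the same treatment estimate.
- **Switch:** judge normality on the residuals of this model by a rule fixed in advance, in place of a test plus an inspection of the histogram.
- **Rank branch:** if the rule is met, apply the Mann-Whitney test to the residuals of V5 regressed on V2 and the two strata, without arm. State whether that regression uses all three arms or only the two compared.
- **Sensitivity:** keep the unadjusted t-test and Mann-Whitney test on the change.

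The cost is wording and slightly more analysis work, with no new data or patients. The model spends 3 degrees of freedom on covariates and can lose up to about 1 to 3 points of power in very small arms where the V2 slope is near 1.

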1.2 STUDY DESIGN

This is a monocentric study in a placebo-controlled, randomized design with three treatment groups. The administration of the investigational drugs is conducted in a double-blind manner with placebo, acamprosate, or calcium carbonate.

The comparison will be made between the calcium group and the placebo group, as well as between the acamprosate group and the placebo group.

Self-infusion of the NIMP (alcohol / saline solution) will be conducted openly regarding the preparation and single-blind regarding the dosage during visits alcohol self-administration visits V2 and V5.

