6.7 INTERIM ANALYSES

No interim analyses are planned

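### Fixed 0.025 for each of the two primary tests is valid, but Holm's step-down would confirm a second effective drug more often within the same 5% family-wise limit

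*SAP*

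**What the plan says.** Section 1.2 sets out two contrasts with a common control: "The comparison will be made between the calcium group and the placebo group, as well as between the acamprosate group and the placebo group". Section 6.4, under "Testing the two primary hypotheses", lists H1 (acamprosate versus placebo) and H2 (calcium versus placebo) as separate confirmatory claims. Each is tested by a t-test, or by a Mann-Whitney test if normality fails. The level is then fixed: "The significance level is 0.025, as two null hypotheses are tested in the confirmatory analysis".

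The SAP contains no ordering of the two hypotheses, no step-down rule and no passing of alpha from one to the other. Section 6.7 rules out other use of alpha: "No interim analyses are planned". The overall 5% is not written out, but it is what two tests at 0.025 add up to.

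**The concern.** A fixed 0.025 for both tests means that, once one drug has been confirmed, the other is still held to half the level it could be tested at without breaching 5% overall. Suppose the p-values were 0.010 and 0.035. Section 6.4 as written confirms one drug. Holm's procedure confirms both, under the same family-wise limit and with no additional participants.

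What is at stake is the second confirmatory result in a trial that tests two hypotheses and could find that both drugs work. The validity of a result confirmed at 0.025 is not in question.

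**Working it through.** **Reproducing the plan's figure.** 0.05 / 2 = 0.025, which matches section 6.4 exactly.

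**Inputs.** From the SAP: two hypotheses, 0.025 each, a shared placebo arm, no interim looks. Section 1.1 gives a relevant difference of 60 work trials, but the SAP gives no SD, sample size, power or allocation ratio. The following are therefore assumptions:
- Equal arms. The two test statistics then correlate at √(½ × ½) = 0.5.
- Two-sided tests. Section 6.4 does not state sidedness.
- Power per comparison at 0.025 of 50% to 90%.

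**Rules compared.**
- Bonferroni: reject each hypothesis if p ≤ 0.025 (|Z| > 2.241).
- Holm: reject the hypothesis with the smaller p if that p ≤ 0.025. Only then reject the other if its p ≤ 0.05 (|Z| > 1.960).

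**Why Holm keeps 5%.** If both nulls are true, a false rejection requires the smaller p to be ≤ 0.025, which has probability at most 0.025 + 0.025 = 0.05. If one null is true, falsely rejecting it requires its own p ≤ 0.05. Neither step uses the correlation, so the shared placebo arm and the choice of t-test or Mann-Whitney do not affect the argument.

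**Power.** The mean of each test statistic is 2.241 + z(power); at 80% this is 2.241 + 0.842 = 3.083. Bivariate normal simulation with correlation 0.5 and 2,000,000 draws, both drugs equally effective, gives (Bonferroni → Holm):

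| Assumed power at 0.025 | Per hypothesis | Both confirmed |
|---|---|---|
| 50% | 50% → 55.3% | 33.4% → 43.8% |
| 60% | 60% → 65.6% | 44.0% → 54.9% |
| 70% | 70% → 75.4% | 55.8% → 66.3% |
| 80% | 80% → 84.6% | 68.8% → 77.9% |
| 90% | 90% → 93.1% | 83.3% → 89.4% |

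Numerical integration of the bivariate normal agrees to within about 0.1 point.

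- At least one rejection: identical under both rules at every power level, for example 91.3% at 80%. Holm's first step is the Bonferroni test.
- Second effect 70% as large as the first, with the first at 80%: power for the second rises from 46.7% to 56.0%.
- Only one drug works: the power gain for that drug is 0.1 to 0.2 points.
- One-sided reading, 80% power: 85.1% per hypothesis and 78.8% for both under Holm. The conclusion does not depend on sidedness.

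**Error rates (two-sided).** With neither drug effective, family-wise error is 4.65% under either rule. With one drug effective, the false-positive rate for the other is 2.5% under Bonferroni. Under Holm it is 4.2% when the effective drug has 80% power, and it approaches 5% as that power approaches 100%.

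**The case against.** The strongest reply is that nothing here is wrong. Section 6.4 names two hypotheses, divides alpha between them, gives the reason and controls family-wise error. That stands: the point concerns efficiency only. A reader might infer that the 0.025 rule is an error or leaves the 5% unprotected, and the SAP does not support that.

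A second reply is that section 1.1 joins the two comparisons with an "or" and defines the relevant change as occurring in one of the active groups. On that reading the power that matters is the chance of at least one rejection, and Holm does not alter it. This also stands, so it would be too strong to say that the plan loses power for its overall question. It does not dispose of the point, because section 6.4 lists H1 and H2 as separate confirmatory claims and the second of them does lose power.

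A third reply is that Bonferroni buys something: stricter protection for the second claim (2.5% rather than up to 5%), and 97.5% intervals that match the tests. Both are real, so it cannot be said that the fixed level has no benefit in error control. But the stricter protection goes beyond the family-wise limit that the plan's own reasoning implies, and the interval mismatch is a matter of reporting.

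**Conclusion.** The point holds as a minor, optional improvement. Within a 5% family-wise limit, Holm rejects whatever the fixed 0.025 rule rejects and sometimes more. That ordering does not depend on the power, the allocation ratio or the sidedness.

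The size does depend on assumptions. With equal arms, two-sided tests, both drugs equally effective and 50% to 90% power per comparison, the gain is about 3 to 5.5 points per hypothesis and about 6 to 11 points for confirming both. A reader might infer a general gain for the trial. The figures do not support that: the benefit is confined to the second hypothesis once the first has been rejected, and it is negligible if only one drug works.

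**What to change.** Before unblinding, replace the fixed level in section 6.4 with a statement that the two hypotheses are tested by Holm's procedure: the smaller p-value is compared with 0.025 and, only if that is significant, the other is compared with 0.05. If 97.5% confidence intervals are reported for both contrasts, add that they may include zero when a hypothesis is rejected at the second step.

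The cost is one or two sentences and a check that the protocol, which is not shown, states the same rule. Sample size and data collection need not change, because the first step remains at 0.025. The price in error terms is the higher false-positive rate for an ineffective second drug, still at most 5%. The rule must be fixed in advance; it could not credibly be adopted once results are known. The sidedness of the tests is a separate matter, which this change does not settle.
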